The University of Texas Medical Branch Galveston
Research Protocol

**Estimating Blood Loss Using Triton™ in Vaginal Deliveries: A Validation Trial
(ELUSIVE Trial)**

Principal Investigator: [name]

Co-Investigators: [name], CNM, & [name].

Funding: Department of Maternal Fetal Medicine

1. Introduction/Background/Purpose:

Postpartum hemorrhage (PPH) is the leading cause of maternal mortality in low-income countries and the primary cause of nearly one quarter of all maternal deaths globally (1). An estimated blood loss (EBL) in excess of 500 mL following a vaginal birth has often been used for the definition of PPH, but the average volume of blood lost at delivery can approach these amounts when actually measured rather than estimated (2). More than half of all maternal deaths occur within 24 hours of delivery, most commonly from excessive bleeding (3). Worldwide, 140,000 women succumb to postpartum hemorrhage each year. The most common antecedents to postpartum hemorrhage are uterine atony, placental disorders, and trauma during delivery. Improving maternal health worldwide is one of the WHO's 8 Millennium Development Goals. The prevention and treatment of PPH is an essential step towards the achievement of that goal (4).

Estimates of blood loss at delivery are notoriously inaccurate, with under-estimation more common than over-estimation (5). Traditionally, the clinicians performing the vaginal delivery would estimate the blood loss by visually assessing the blood collected in the delivery drape drain and counting the number of lap sponges used thru out the delivery. Current detection and management of hemorrhage is heavily based on clinical judgment, which often leads to delay in recognition and intervention. Often, interventions such as fluid resuscitation and blood transfusion are not initiated until significant hemorrhage has already taken place. The traditional method for estimating blood loss is based on the clinician and nursing staff's subjective assessment that is severely limited by human error and the presence of large volumes of amniotic fluid (6).

Early detection and treatment of this potentially life-threatening obstetric complication is of utmost importance in the field of obstetrics. Simulations and didactic training have been shown to improve visual estimations, but there are still poor associations between experience level and accuracy, and a significant decay in blood loss estimation skills over time (7).

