2. **Summary of project:** This study will be a prospective cohort study. Patients who meet criteria for inclusion in the study will be approached for participation at same day of admission. Written informed consent will be obtained from the patients by the Co-PI and by the study collaborators. If patients agree to participate, a CBC (complete blood count) will be obtained via venous puncture routine in our facility as part of the admission labs which will be around 10 cc of blood. The device will be used during the delivery in laboring room. The device will be used to assess QBL by the research staff only and results/ QBL assessment will be masked to the clinical team. Unmasking will only occur following study completion with purpose to perform data analysis. Patient management will be according to the clinical team without the knowledge of the QBL. All patients undergo a CBC postpartum as part of post-partum evaluation, this will also be performed by venipuncture where 10 cc of blood will be collected. The drop in Hgb (Δ Hgb) between the pre and post partum CBCs will be calculated for each patient. The post-partum CBC will be collected approximately 24-30 hours from delivery as standard in our unit. The blood will be collected from each patient by the nursing staff who are experienced in withdrawing blood. Patients will be divided into quartiles of Δ Hgb. Cases will be those patients whose Δ Hgb is in the upper quartile, while controls will be those patients whose Δ Hgb is in the lower 3 quartiles. We will be comparing visual EBL by standard clinical assessment versus the QBL result from the device between cases and controls.

The Triton L&D system which comprises of the device, software analysis and staff training will be supplied by the manufacturer free of charge. Research staff will be trained by the manufacturer. We will be offering our skills, fellows, midwives and residents, who will be collecting data and we will be performing the data analysis. Results will be available to the manufacturer after results are completed. The results of this study will be presented in conferences or published in a peer-review journal.

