Demographic information will be obtained from the electronic medical record. The data will be kept on a password secured UTMB computer. An encrypted USB flash drive will be used to transfer data. The data will be identified and linked to the patient using the medical record number (MRN). During data analysis, all patient identifiers will be deleted.

3. Study procedures: VISIT#1

3.1 Screening, Recruitment and Consenting: When a patient meets inclusion criteria for participation in our study, the obstetrical team will contact the research team. Written informed consent will be obtained from the patient by the PI, study coordinator, or collaborator. Study participation will be completed when the patient is discharged from the hospital. The data collected will be kept on a password secured UTMB computer. An encrypted USB flash drive will be used to transfer data. The data will be linked via MRN, which is needed to access the demographic data and will be deleted when the data is analyzed. Our target sample size is 556 subjects.

3.2. Baseline procedures: In some patients, there will be no baseline procedures aside from using the masked device for assessment of QBL. Every effort will be made to mask the clinical staff from the QBL information so as not to affect the standard assessment of visual EBL and medical decision making. During blood loss assessment, clinicians will be instructed not to place any sponges and other junk or materials into the calibrated v-drape following placental delivery (before placenta is delivered this is allowed), since it can artificially inflate or interfere with the accuracy of QBL. Subjects, where this protocol deviation occurs, will be removed from the final analysis and replaced by other cases in order to meet our final sample size. Neither the subject's insurance nor the subject will be responsible for any charges relating to tests done only for research.

3.3. Study visits/Follow-up: One study visit will be needed during the trial. The subject participation will be considered complete when the subject is discharged home.

3.6. Withdrawals: Subjects who withdraw from the study after inclusion will be excluded from further follow-up. Data collected until the time of withdrawal will be analyzed.

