3.7 Outcomes

- **Primary outcome:** Differences in blood loss between cases and controls using clinical estimate (visual EBL) versus device assessment (QBL).
- **Secondary outcomes:** System performance (ROC sensitivity analysis and correlation). Delta hemoglobin, hemorrhage recognition (defined as >500 ml blood loss), transfusion requirements (timing, rate, dose, etc.), administration of uterotronics, colloid resuscitation, post-partum hemorrhage or hemorrhagic shock.

4. Criteria for inclusion of subjects:

Pregnant women between the ages of 18-50.
Plan of care is vaginal delivery.

5. Criteria for exclusion of subjects:

- Incarcerated patients.
- Patient unwilling or unable to provide consent.
- Intrauterine fetal demise (no fetal heart beat identified and documented by two physicians).
- Placenta previa or other known placental anomalies.
- Any contraindications to vaginal delivery.
- Enrolled in another trial that may affect outcome.

6. Sources of research material: Electronic medical records.

7. Recruitment methods and consenting process: See 3.1 above.

8. Potential risks

8.1 Loss of confidentiality: Any time information is collected, there is a potential risk for loss of confidentiality. Every effort will be made to keep the subject's information confidential; however, this cannot be guaranteed.

9. Potential benefits: With the QBL approach of assessing blood loss more objectively during vaginal delivery, there are many potential benefits to future patients, including: decrease in the delay in diagnosis of hemorrhagic shock, decrease in delay in interventions and improved postpartum surveillance. In addition, this data will be useful in designing a level 1 trial to measure outcomes such as transfusion rates, transfusion complications, hemorrhage and maternal death.

10. Data monitoring: The PI, research coordinator, and collaborators will ensure that all aspects of data quality adhere to the study design. This will include monitoring for adherence to consent procedures, inclusion and exclusion criteria, valid abstraction, correct entry, timeliness and

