responsiveness to data queries. Data will be collected and stored with the participant ID code only. The master enrollment log linking patient identifiers with study ID numbers will be kept in a password protected database on the Ob/Gyn department's internal server. Several data collection forms will be used. Data on these forms will be devoid of personal identifiers and will be securely stored at the division offices. The research coordinator will be available to monitor the data and correct any discrepancies based on source documents if needed.

11. Procedures to maintain confidentiality: Each subject will be assigned a study number with personally identifiable information deleted or removed. If needed, charts will be reviewed in the medical records area. Subjects' information will be de-identified and tagged with a number. Data will be collected and stored on a UTMB password-protected computer.

Statistical approach: We will be performing a prospective study. After defining cases and controls using the cutoff of upper quartile for pre- to postop- hemoglobin drop. We will use univariable and multivariable analysis to check for association between both blood loss assessment techniques using the device and the subjective clinical assessment among our cases and controls. We will be comparing cases versus controls (two groups) and EBL/QBL (continuous variable and primary outcome) hence t tests/means were used for our sample calculation; For the purpose of the study, we believe a sample size of 500 will be able to evaluate our primary outcome. Accounting for 10% loss of data or follow-up: **N total is 556 subjects.** This was based on a study of 30,937 patients having vaginal deliveries using the Triton™ System (the mean measured blood loss was 383.87ml with a standard deviation of 330.52 ml (unpublished data supplied by the manufacturer). For a power of 80% and alpha of 0.05 and 25% effect size 1: 3 allocation (25%ile versus 75%ile PP delta hemoglobin):

Estimated sample sizes for a two-sample means test
t test assuming $sd_1 = sd_2 = sd$
 $H_0: m_2 = m_1$ versus $H_a: m_2 \neq m_1$

Study parameters:

```
alpha = 0.0500
power = 0.8000
delta = -95.9700
m1 = 383.8700
m2 = 287.9000
sd = 330.5200
N2/N1 = 3.0000
```

Estimated sample sizes:

N = 500
N1 = 125
N2 = 375

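### The haemoglobin drop that defines cases has no rule for women transfused before the postpartum CBC, so some heavy bleeders can be labelled controls (minor, cheap to fix)

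*Combined protocol and SAP*

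**What the plan says.** Section 2 (Summary of project) describes the drop in haemoglobin "between the pre and post partum CBCs will be calculated for each patient". On the second sample it says: "The post-partum CBC will be collected approximately 24-30 hours from delivery as standard in our unit". Then: "Patients will be divided into quartiles of" that drop. The upper quartile are cases and the lower three are controls. The Statistical approach repeats the rule: "After defining cases and controls using the cutoff of upper quartile for pre- to postop- hemoglobin drop".

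Section 2 leaves patient management to the clinical team, who do not see the QBL, so a transfusion can precede the second CBC. Section 3.7 lists among the secondary outcomes "transfusion requirements (timing, rate, dose, etc.), administration of uterotronics, colloid resuscitation".

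The exclusion criteria (section 5) do not mention transfusion. The one stated removal from the final analysis, in section 3.2, concerns material placed in the drape after placental delivery: "Subjects, where this protocol deviation occurs, will be removed from the final analysis and replaced by other cases". The multivariable analysis names no covariates. The case label feeds the primary comparison (section 3.7 and Statistical approach) and the ROC comparison of EBL with QBL.

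**The concern.** The haemoglobin drop stands in for true blood loss when the groups are formed. Transfusion before the second CBC raises the second value and breaks that link, most plausibly in the women who bled most. The Introduction says of current practice: "Often, interventions such as fluid resuscitation and blood transfusion are not initiated until significant hemorrhage has already taken place". A woman with a large loss can then fall into the lower three quartiles, and a woman with a smaller loss takes her case place. A transfusion after the CBC does not affect the label.

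The error is in the grouping variable, so covariates in a regression would not repair it. It reaches the primary contrast and both AUCs, and it concerns the women in whom accurate measurement matters most. Without a rule, their handling could be chosen after the QBL values are known.

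**Working it through.** **1. The plan's own figure.** Inputs from the Statistical approach: two-sided alpha 0.05, power 0.80, difference 95.97 mL (25% of 383.87), SD 330.52 mL, allocation 1:3.

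n1 = (1 + 1/3) × (1.960 + 0.842)² × (330.52/95.97)² ≈ 124.1, so 125 cases and 375 controls, N = 500. Then 500/0.90 = 555.6, so 556. Both figures reproduce; this point does not touch them.

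**2. Effect of one mislabelled woman.** Suppose a true case with loss L is labelled a control and is replaced among the cases by a woman at the planned control mean of 287.9 mL. The contrast falls by (L − 287.9) × (1/125 + 1/375).
- L = 1000 mL (assumed): 712.1 × 0.010667 = 7.6 mL.
- L = 1500 mL (assumed): 1212.1 × 0.010667 = 12.9 mL.

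**3. Power at the planned contrast.** Simulated loss is lognormal with the plan's mean and SD. Its correlation with the drop (about 0.19 on the log-loss scale) is set to give 96 mL and an AUC of 0.590. Assumed: the heaviest 0.5, 1 or 2% are transfused before the CBC, which lowers their drop by 1 SD of the drop. Power ≈ Φ(d/SE − 1.96), with SE = 330.52 × √(1/125 + 1/375) = 34.14 mL.

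| Transfused (of 500) | Contrast d, mL | d/SE | Power |
|---|---|---|---|
| none | 95.97 | 2.81 | 0.80 |
| 0.5% (2.5) | 77-84 | 2.26-2.46 | 0.62-0.69 |
| 1% (5) | 65-71 | 1.90-2.08 | 0.48-0.55 |
| 2% (10) | 48 | 1.41 | 0.29 |

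The lower end of each range ranks women by loss alone; the upper end ranks by loss and drop together. With the combined ranking, the AUC goes from 0.590 to 0.588/0.584/0.574. As an extreme, if transfusion hid the drop completely, the contrast would be 61/39/6 mL and the AUC 0.579/0.568/0.549.

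**4. Power if the drop tracks loss more closely.** With correlation 0.4 the starting contrast is 211 mL. The same 1 SD offset (combined ranking) gives 204/192/169 mL, AUC 0.693 falling to 0.691/0.689/0.680, and power of at least 0.99.

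**5. Both methods together.** A second model derives the drop from loss. Assumed: admission haemoglobin 12 ± 1 g/dL, blood volume 5500 ± 800 mL, noise of 0.5 or 1.1 g/dL on the drop, QBL error 25% CV, EBL at 0.75 of loss with 50% CV. The top 0.5-2% by EBL, true loss or low haemoglobin are transfused, with a rise of 1 or 2 g/dL. Without transfusion, the EBL/QBL contrasts are 333/444 mL (noise 0.5) or 221/296 mL (noise 1.1).
- 0.5-1% transfused: 0.0-2.6 of 125 case places change hands; AUCs fall 0.000-0.011.
- 2%, rise 1 g/dL: 1.0-2.8 places; AUCs fall 0.001-0.012.
- 2%, rise 2 g/dL: about 4-6 places; AUCs fall 0.007-0.026; the EBL contrast falls 5-31% and the QBL contrast 5-22%.
- The QBL-minus-EBL AUC gap moves by −0.001 to +0.004, against a sampling SD of 0.017-0.019 in trials of 500.
- Power of both t tests stays at or above 0.996, but only because these starting contrasts exceed 220 mL.

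**The case against.** The strongest reply is that this is too small to matter. The documents give no transfusion rate, trigger or timing. Listing transfusion as a secondary outcome shows that it will be recorded, not that many women will receive it before the CBC, and the Introduction describes practice in general, not this cohort. At 0.5-1% transfused, the AUC loss is at most 0.011 in the two-method model, under half the sampling SD of a single AUC (0.022-0.030). Most transfused women keep their label in most scenarios: with a 1 g/dL rise, 0-28% move from case to control; with 2 g/dL, 11-60%. Fluids or colloid can dilute haemoglobin and act the other way. If the top 5% all had a further dilutional drop of 0.5 g/dL, the net AUC change at 0.5-1% transfused would run from −0.005 to +0.012, so even its direction is uncertain.

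All of this stands, and it keeps the point minor. It does not supply the missing rule. Nor can the plan be called safe on power: that reassurance needs a contrast well above the one the trial was sized for.

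A reader might also infer that the omission biases the comparison of EBL with QBL. The documents do not support that. Both methods are judged against the same label, and the simulated gap moves by far less than its sampling error.

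**Conclusion.** The omission is real. The case rule is stated in full, twice, and followed as written it can place some heavy bleeders among the controls. The expected result is dilution of the primary contrast and of both AUCs, of unknown and possibly small size.

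Under the assumed rates of 0.5-2%, with rises of 1-2 g/dL or a 1 SD offset, the AUC loss is about 0.000-0.026. The effect on power depends on the true contrast. It is negligible well above 200 mL under these assumptions; at 95.97 mL, power could fall from 0.80 to about 0.6-0.7, 0.5 or 0.3 at 0.5, 1 or 2% transfused.

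Two stronger readings are not supported: that the primary test is defeated, which would need a transfusion rate and a true contrast the documents do not give, and that every transfused woman is misclassified. This is a minor, cheap improvement.

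**What to change.** Add a few sentences to the Statistical approach before the QBL values are released; section 2 allows this, since "Unmasking will only occur following study completion with purpose to perform data analysis".

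- For women transfused before the postpartum CBC, add a stated haemoglobin increment per recorded unit back to the measured drop, then form the quartiles.
- Report how many women this affects and how many received colloid.
- Repeat the primary and AUC comparisons with the uncorrected drop, with these women classed as cases, and once with a different increment (for example half).
- Keep the CBC draw time alongside the transfusion time, so that transfusions before and after the CBC can be told apart.

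The cost is analysis wording and one extra time field from the medical record. No visit, test, patient or aspect of care changes.

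The downsides should be stated. The increment is an assumption, and adding it back does not correct for dilution. In the 2%, 2 g/dL illustration, adding back half the true rise still leaves AUCs 0.001-0.012 low, against 0.007-0.025 uncorrected in the same set of runs. Classing all these women as cases changes AUCs by −0.001 to +0.011 and could favour EBL by up to 0.002 if EBL influences who is transfused. Excluding them is not a good main rule: it removes the largest losses and lowers AUCs by 0.012-0.023 at 2%.

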The Triton L&D system (Gauss Surgical, Inc., Menlo Park, CA) is an FDA-cleared mobile application on a tablet computer (iPad) that facilitates quantification of blood loss (QBL) by providing an easy to use process and user interface. Dry weights of all potential blood containing substrates are built-in to the device allowing batch weighing with automatic subtraction of dry weights. There is also a V-drape simulator accounting for collected fluids with automatic subtraction of a measured amount of amniotic fluid.

QBL is not regularly used at UTMB. Although widely recommended, little data is available to support its use in the obstetrical population. We believe that gathering further evidence regarding its value is appropriate.

Our hypothesis is that use of this device for QBL will enable clinicians to objectively measure blood loss in real-time.

This study will be a prospective cohort study, in which we will evaluate two methods of evaluating blood loss during vaginal delivery (usual visual EBL assessment versus Device QBL). Of note, the subjects consented will be used as self-controls.

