We will also be using multiple model correlation (correlation coefficient) (secondary outcome) between QBL Device and EBL Standard. We will also perform ROC curve analysis (secondary outcome) to compare the area under the curve (AUC) to predict Δ Hgb in the upper quartile by clinical estimate versus device assessment. The coefficient of multiple correlation takes values between 0 and 1; a higher value indicates a better predictability of the dependent variable (QBL Device) from the independent variable (EBL standard).

REFERENCES

1. AbouZahr, C. (2003). Global burden of maternal death and disability. *Br Med Bull*, 67, 1-11.
2. Chesley, L. C. (1972). Plasma and red cell volumes during pregnancy. *Am J Obstet Gynecol*, 112(3), 440-450.
4. WHO Guidelines Approved by the Guidelines Review Committee: WHO recommendations for the prevention and treatment of postpartum hemorrhage. Geneva, Switzerland, 2012.
5. Bonnet, M. P., & Benhamou, D. (2016). Management of postpartum haemorrhage. *F1000Res*, 5. doi:10.12688/f1000research.7836.1.
6. Satish, Siddarth MS; Deckers, Elizabeth A. MD; Philip, Bridget M. MD; Ting, Vicki MD; Weinberg, Joseph T. BA. Novel System for Rapid Assessment of Blood Loss in Elective Surgery and Cesarean Delivery. *Obstet Gynecol*. 2014 May;123 Suppl 1:170S.
7. Dildy, G. A., 3rd, Paine, A. R., George, N. C., & Velasco, C. (2004). Estimating blood loss: can teaching significantly improve visual estimation? *Obstet Gynecol*, 104(3), 601-606. doi:10.1097/01.aog.0000137873.07820.34.
10. Holmes, A. A., Konig, G., Ting, V., Philip, B., Puzio, T., Satish, S., & Waters, J. H. (2014). Clinical evaluation of a novel system for monitoring surgical hemoglobin loss. *Anesth Analg*, 119(3), 588-594. doi:10.1213/ane.000000000000181.

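### QBL and EBL are measured in the same women, but the plan commits to no paired difference, limits of agreement or >500 mL cross-table between them

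*Combined protocol and SAP*

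**What the plan says.** The title calls the study a validation trial. Section 1 sets visual EBL against device QBL in the same patients: "Of note, the subjects consented will be used as self-controls". It also says: "Estimates of blood loss at delivery are notoriously inaccurate, with under-estimation more common than over-estimation". Section 2 has research staff measure QBL, masked from the clinical team, and defines cases as women in the top quartile of hemoglobin drop.

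The analyses that involve both methods are:

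- **Primary outcome (3.7):** "Differences in blood loss between cases and controls using clinical estimate (visual EBL) versus device assessment (QBL"). Section 2 describes the same case-control comparison.
- **Secondary outcomes (3.7):** system performance by ROC and correlation. The list also has "hemorrhage recognition (defined as >500 ml blood loss"), with no statement of how the two methods will be compared on it.
- **Statistical approach, association:** "univariable and multivariable analysis to check for association between both blood loss assessment techniques using the device and the subjective clinical assessment". The sentence goes on to refer to the cases and controls, and no model is given.
- **Statistical approach, direct comparison:** "We will also be using multiple model correlation (correlation coefficient) (secondary outcome) between QBL Device and EBL Standard". A higher coefficient is to be read as better prediction of QBL from EBL.
- **Statistical approach, ROC:** AUCs are compared for predicting a hemoglobin drop "in the upper quartile by clinical estimate versus device assessment".

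No section specifies a within-woman QBL minus EBL difference, an interval for it, limits of agreement, or a cross-classification of the two methods at 500 mL.

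**The concern.** The error that the protocol attributes to blood loss estimates is mainly systematic, and correlation is blind to systematic error. With the single predictor that the plan names, the multiple correlation is just the absolute value of r. It stays the same however far EBL lies below QBL, provided the two rise together.

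As written, the trial could report a high correlation and similar AUCs without saying by how many mL the methods differ, how far apart they can be in one woman, or how often they disagree on whether a woman lost more than 500 mL. A reader of a validation study would look for these results, and the paired data to produce them will already have been collected.

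**Working it through.** **1. The plan's own figure.** Inputs from the Statistical approach: difference 95.97 mL, SD 330.52 mL, two-sided alpha 0.05, power 0.80, allocation 1:3.

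n1 = (1 + 1/3) × (1.960 + 0.842)² × (330.52/95.97)² = 1.333 × 7.849 × 11.86 = 124.1, so 125 cases and 375 controls, N = 500. Exact t-test power at 125/375 is 80.1%. With 10% loss, 500/0.9 = 556. Both figures reproduce. They size a case-control contrast and say nothing either way about agreement.

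**2. What each planned quantity can detect.** Take any EBL and lower it by a constant c, or multiply it by a factor k below 1.

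| Quantity | EBL − c | k × EBL |
|---|---|---|
| Correlation with QBL | unchanged | unchanged |
| AUC for upper-quartile drop | unchanged | unchanged |
| Case-control difference, mL | unchanged | multiplied by k |
| Mean by method | shifts | shifts |

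A simulation with noise shows the same. Assumptions: gamma QBL with the plan's mean and SD, EBL error SD 200 mL. The correlation is 0.855 whether EBL is unbiased, 150 mL low or halved, while the mean QBL minus EBL difference is 0, 150 and 192 mL.

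**3. Size at the 500 mL threshold.** From the plan: "the mean measured blood loss was 383.87ml with a standard deviation of 330.52 ml". Assume QBL is lognormal.

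- CV = 330.52/383.87 = 0.861.
- Log-SD = sqrt(ln(1 + 0.861²)) = 0.745.
- Log-mean = ln(383.87) − 0.745²/2 = 5.673.
- P(QBL > 500) = 1 − Φ((ln 500 − 5.673)/0.745) = 23.4%, or 117 of 500.

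If EBL = k × QBL, the threshold becomes 500/k. If EBL = QBL − 50, it becomes 550.

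| Assumed EBL | >500 mL by EBL | Of 500 women | r |
|---|---|---|---|
| 0.9 × QBL | 19.2% | 96 | 1 |
| 0.7 × QBL | 11.4% | 57 | 1 |
| 0.5 × QBL | 4.9% | 24 | 1 |
| QBL − 50 mL | 19.6% | 98 | 1.00 |

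For the primary outcome, assume a latent correlation of 0.20 between QBL and hemoglobin drop, which gives a difference near the plan's 96 mL. A constant 50 mL under-reading leaves the case-control difference at 101.3 mL by QBL and 101.2 mL by EBL. A factor of 0.7 does show: 100.6 against 70.4 mL.

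**4. Spread in individual women.** Assume no bias and equal log-SDs. The 95% limits for the QBL/EBL ratio are exp(±1.96 × 0.745 × sqrt(2(1 − r))), with r on the log scale.

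| Log-scale r | mL-scale r | Ratio limits, either way |
|---|---|---|
| 0.5 | 0.43 | factor 4.3 |
| 0.7 | 0.64 | factor 3.1 |
| 0.9 | 0.87 | factor 1.9 |

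**5. What could be rebuilt from summaries.** The mean gap follows by subtracting the means by method. The paired SD follows from SD_diff² = SD_Q² + SD_E² − 2 × r × SD_Q × SD_E, if a Pearson r and both SDs are reported. With equal SDs of 330.52 mL, N = 500 and mL-scale r of 0.43, 0.64 or 0.87, the paired 95% CI half-width for the mean difference is 31, 25 or 15 mL. It is 41 mL if the two means are treated as independent. The ratio-scale limits and the discordant cells at 500 mL cannot be rebuilt this way.

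**6. Power of a test at 500 mL.** Under an assumed factor of 0.9, the exact McNemar test at N = 500 has simulated power of 45%, 53% or 77% at log-scale r of 0.5, 0.7 or 0.9. At a factor of 0.7 it is about 100%.

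**The case against.** The strongest defense is that the plan validates both methods against an external reference, the hemoglobin drop. Its own background calls estimates of blood loss inaccurate, so agreement with EBL is not the test that QBL has to pass. This stands: agreement statistics describe disagreement and cannot show which method is nearer the truth.

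Three stronger readings are tempting, and the documents do not support them.

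- **That the methods are only ever correlated.** They are not. Section 2, the primary outcome and the AUC comparison all set EBL beside QBL through the case-control split.
- **That the association analysis is a second correlation of QBL with EBL.** The sentence ends with the cases and controls, so it may equally mean the association of each technique with case status. It is ambiguous and is not counted here.
- **That the paired difference would be lost.** On the mL scale it could be rebuilt as in step 5. However, the plan does not promise a Pearson coefficient or SDs by method, and ratio-scale spread and disagreement at 500 mL would still be missing.

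It is also fair to say that the scenarios with r = 1 are extreme for a visual estimate. They show what correlation can miss and do not predict what this trial will find.

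**Conclusion.** The point holds as an omission in reporting. The only clearly direct QBL-EBL analysis is a correlation, which cannot detect the under-estimation that the protocol itself describes. The plan commits to no paired difference, limits of agreement or cross-table at >500 mL.

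The possible size is material. Under the lognormal assumption, a 10% under-reading moves 23.4% above 500 mL to 19.2%, and a 30% under-reading moves it to 11.4%, with the correlation unmoved. The documents give no EBL mean, no EBL SD and no QBL-EBL correlation, so the bias sizes, correlations and equal SDs are all assumptions.

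A reader might infer that the sample size or the planned analyses are wrong. They are not: N = 500 reproduces, and the quartile case-control and ROC analyses answer a different, legitimate question. This is a cheap improvement.

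**What to change.** In the Statistical approach, keep the QBL-EBL correlation and add two descriptive secondary analyses:

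1. The mean QBL minus EBL difference with a paired 95% CI and Bland-Altman limits of agreement. Pre-specify the ratio (log) scale alongside the mL scale, so that the scale is not chosen after seeing the data, and state a rule for zero values.
2. The paired 2x2 table of >500 mL by QBL and by EBL, with the paired difference in proportions and its 95% CI. Any McNemar test should be labelled supportive, given its power of about 45 to 77% under an assumed 10% under-reading.

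State that both describe disagreement, and that the question of which method is nearer the truth stays with the hemoglobin-drop analyses.

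The cost is some plan wording and a few lines of code, with no new data and no change to N. The downside is two more secondary results to report.
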